#### **5.1 Inclusion criteria**

Participants eligible for inclusion in this study must meet **all** of the following criteria:

1. Signed informed consent and/or assent (where applicable) must be obtained prior to study participation. Participant (and parent/legal guardian) must be able to understand and provide informed consent and assent, as applicable. If a minor participant providing assent reaches the age of legal majority (as defined by local law), he/she must be re-consented (ICF) at the next study visit.
2. Male or female participants who are 6 to 55 years of age at the time of signing informed consent/assent.
3. Documented medical history of allergy to peanuts or peanut-containing foods.
4. Positive peanut-specific IgE (peanut sIgE), ≥ 0.35 kUA/L at Screening Visit 1.
5. Positive skin prick test (SPT) for peanut allergen at Screening Visit 1. This is defined as the average diameter (longest diameter and mid-point orthogonal diameter) ≥ 4 mm wheal compared to the negative control.

6. A positive peanut DBPCFC at baseline (Screening Visit 2, Part 1 and Part 2 DBPCFC) defined as the occurrence of dose-limiting symptoms at a single dose  $\leq$  100 mg of peanut protein. Eligibility to proceed with the DBPCFC requires presence of all inclusion and absence of all exclusion criteria.
7. Participants must weigh  $\geq$  20 kg at Screening Visit 1.
8. Participants must be able to receive injections (study treatment), participate in the DBPCFC, and must be willing to continue avoiding exposure to peanuts and any other foods that they are allergic to throughout this study.

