The Food Allergy Independent Measure (FAIM) reflects the participant’s perceived food allergy severity and food allergy-related risk. The total score for the FAIM ranges from 1 to 7 (i.e., from ‘limited’ to ‘the greatest’ severity perception). If less than 80% of the items are complete, then the total score will not be calculated. Similarly, if less than 80% of the items within a domain are complete, then the domain score will not be calculated. (van der Velde et al 2010)

The Food Allergy Quality of Life-Parental Burden (FAQL-PB) Questionnaire is a self-administered, disease-specific instrument developed to measure the effect of pediatric food allergy on HRQoL among caregivers. The instrument includes 17 items investigating the effect of having a child with food allergy on family/social activities, school, meal preparation, health concerns and emotional issues, using a 7-point Likert scale (Cohen et al 2004).

The SF-36v2® Health Survey is a 36-item instrument for measuring health status and outcomes via participant self-report. It is designed for use in surveys of general and specific populations, health policy evaluations, and clinical practice and research. The SF-6Dv2 (Brazier et al 2020) will be derived from the SF-36v2 (Maruish 2011) for health economic evaluations. The SF-6Dv2 captures the impacts of food allergy on social activities and depression/nervousness.

All questionnaires will be completed in the language most familiar to the respondent. The same parent/caregiver should complete the assessments throughout the study.

The participant should be given sufficient instruction, space, time and privacy to complete the questionnaire during the Randomization visit. The study coordinator should encourage the participants to complete all of the available questionnaires.

[figure not shown]
All participants will complete the PRO questions via a handheld electronic device (note: children aged 6-7 will NOT be completing any PRO measures). Participants will take the device home and should complete them 10 days before Day 1 of the OFC and 3 days after Day 2 of the OFC at 12 weeks and at 52 weeks. If participants experience any difficulties with submission after completing the PROs, they should contact the study staff for assistance. Available training materials related to the administrative procedures of the questionnaires will be provided to the sites.

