## 16.6.2 FAIM-CF: Food Allergy Independent Measure Child Form

Food Allergy Independent Measure – Child Form (8-12 years)											
The following four questions are about the chance that you think you have of something happening to you because of your food allergy. Choose one of the answers. This is followed by two more questions about your food allergy. Answer every question by putting an 'x' in the box next to the proper answer.											
0 never (0% chance)	1 very small chance	2 small chance	3 fair chance	4 big chance	5 very big chance	6 always (100% chance)					
How big do you think the chance is that you ...					0	1	2	3	4	5	6
1. will accidentally eat something to which you are allergic?											
2. will have a severe reaction if you accidentally eat something to which you are allergic?											
3. will die if you accidentally eat something to which you are allergic?											
4. can not do the right things for your allergic reaction should you accidentally eat something to which you are allergic?											
5. How many foods are you unable to eat because of your food allergy?					6. Everyone does things with other people, such as; - playing with friends, - going to a birthday party, - visiting, - staying over with someone for a meal or eating out. How much does your food allergy affect things you do with others?						

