### 16.6.4 FAIM-TF: Food Allergy Independent Measure Teenager Form

Food Allergy Independent Measure – Teenager Form (13-17 years)											
The following four questions are about the chance that you think you have of something happening to you because of your food allergy. Choose one of the answers provided. This is followed by two more questions about your food allergy. Answer every question by putting an 'x' in the box next to the appropriate answer.											
0 never (0% chance)	1 very small chance	2 small chance	3 fair chance	4 great chance	5 very great chance	6 always (100% chance)					
How great do you think the chance is that you ...					0	1	2	3	4	5	6
1. will accidentally eat something to which you are allergic?											
2. will have a severe reaction if you accidentally eat something to which you are allergic?											
3. will die if you accidentally eat something to which you are allergic?											
4. can not effectively deal with an allergic reaction should you accidentally eat something to which you are allergic?											
5. How many products must you avoid because of your food allergy?					6. How great is the impact of your food allergy on your social life?						
 almost none					 negligibly small						
 very few					 very small						
 a few					 small						
 some					 moderate						
 many					 great						
 very many					 very great						
 almost all					 extremely great						

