
3. will die if you accidentally eat something to which you are allergic?
	
 
 								
 
														
															

4. can not effectively deal with an allergic reaction should you accidentally eat something to which you are allergic?
	
 
 								
 
														
															

5. How many products must you avoid because of your food allergy?
	
6. How great is the impact of your food allergy on your social life?
														

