**Food Allergy Independent Measure (FAIM) for children**

Items are answered on a 0-6 or 1-7 point response scale as preferred, with a greater score indicating a higher level of perceived risk. Question 4 must be reverse scored before a Total score is calculated.

	0	1	2	3	4	5	6
1	will accidentally eat something to which he/she is allergic?						
2	will have a severe reaction if he/she accidentally eat something to which he/she is allergic?						
3	Will die if he/she eats something to which he/she is allergic?						
4	will effectively manage a reaction or will receive sufficient help from others if a reaction occurs?						

5. How many foods must your child avoid because of food allergy?	6. How much has your child's food allergy limited the type of activities your child can take part in?
 almost none	 so little he/she doesn't actually notice it
 very few	 very little
 a few	 little
 some	 moderately
 many	 a good deal
 very many	 a great deal
 almost all	 a very great deal

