The number of items and domains varies by FAQLQ instrument administered. Each question is scored on a 7-point scale (coded as 1-7 in analysis, with a higher level indicating greater impairment in HRQoL). The total score is the arithmetic average of all completed items. Domain scores are calculated similarly for each form as following:

FAQLQ-CF: Emotional impact (EI) (item no. 19-24), Allergen avoidance (AA) (item no. 4, 6-10, 15), Risk of accidental exposure (RAE) (item no. 11, 13, 14, 16, 17), Dietary restriction (DR) (item no. 1-3, 5, 12, 18)

FAQLQ-TF: Emotional impact (EI) (item no. 5, 12, 19-23), Allergen avoidance and dietary restrictions (AADR) (item no. 1-4, 6-10, 16), Risk of accidental exposure (RAE) (item no. 11, 13-15, 17, 18)

FAQLQ-AF: Emotional impact (EI) (item no. 5, 24-29), Allergen avoidance and dietary restrictions (AADR) (item no. 1-4, 6, 8-12, 20), Risk of Accidental Exposure (RAE) (item no. 7, 13-18, 21), Food allergy related health (FAH) (item no. 19, 22, 23)

FAQLQ-PF: Emotional impact (EI) (item no. 2, 6, 7, 9-11, 23-28, 30), Food anxiety (FA) (item no. 1, 4, 5, 16, 17, 20, 21, 29), Social and dietary limitations (SDL) (item no. 3, 8, 12-15, 18, 19, 22).

If more than one item in any domain is missing, a domain score should not be calculated for that case. A total score can still be calculated if 20% or fewer of the items are missing.

The FAIM reflects the participant's perceived food allergy severity and food allergy-related risk ([van der Velde, Flokstra-de Blok et al. 2010](#)). Each question is scored on a 7-point scale (coded as 1-7 in analysis, with a greater score indicating a higher level of perceived risk or chance of adverse events occurring). The total score is the arithmetic average of all completed items. If less than 80% of the items within the score are complete, it will not be calculated. Questions 4 and 5 (effectively managing a reaction, receiving sufficient help from others) must be reverse coded.

A threshold of 0.45 points has been suggested and used as a minimal important difference (MID) to interpret clinical relevance ([Dunn Galvin, Cullinane et al. 2010](#)). For FAQLQ and FAIM forms, the 0.45 threshold will be used to interpret the clinical relevance of group-level differences and changes, in addition to within-patient changes.

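### SAP 2.10.1 reverse-codes FAIM items 4 and 5 without naming a form, but on the child, teenager and adult forms both items already score higher for worse status

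*SAP*

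**What the plan says.** SAP Section 2.10.1, under the scoring of the PRO instruments, codes each FAIM question 1 to 7 so that a greater score means more perceived risk, and takes the total as the average of the completed items. It then adds: "Questions 4 and 5 (effectively managing a reaction, receiving sufficient help from others) must be reverse coded". No form is named. The FAIM measures listed by name in that section are the child (CF), teenager (TF) and adult (AF) forms.

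Protocol Section 8.5.1 gives the intended scale: "The total score for the FAIM ranges from 1 to 7", running from limited to greatest perceived severity. It contains no reversal rule. The only reversal instruction in the protocol accompanies the parent-completed FAIM, which is Section D of the FAQLQ-PF in Section 16.6.7: "Question 4 must be reverse scored before a Total score is calculated".

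**The concern.** A reversal rule is needed only for items that run against the scale. On the three participant forms neither item 4 nor item 5 does, so reversing them creates the misalignment the rule is meant to remove. The ideas in the SAP's parenthesis, managing a reaction and receiving help, occur together only in item 4 of the parent form.

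The FAIM total feeds the descriptive summaries, the summaries by Week 12 responder status, the ANCOVAs of change from baseline before and after the Week 12 challenge (SAP 2.10.1.1), and the 0.45-point threshold used to judge clinical relevance for groups and for individual patients (SAP 2.10.1). FAIM-TF and FAIM-AF are both listed in SAP Table 2-2 for the Primary Analysis. A programmer who follows the SAP as written would mis-score both.

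**Working it through.** **Direction of the items on each printed form**

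- FAIM-CF (Protocol 16.6.2), item 4: "can not do the right things for your allergic reaction should you accidentally eat something to which you are allergic", answered from never to always. Item 5 asks how many foods cannot be eaten, from almost none upwards.
- FAIM-TF (16.6.4), item 4: "can not effectively deal with an allergic reaction should you accidentally eat something to which you are allergic". Item 5 asks how many products must be avoided.
- FAIM-AF (16.6.6): item 4 has the same negative wording as the teenager form. Item 5 is "5. How many products must you avoid because of your food allergy", with options rising to almost all.
- Parent form (16.6.7, Section D), item 4: "will effectively manage a reaction or will receive sufficient help from others if a reaction occurs". This is positively worded and does need reversing. Item 5 is again the number of foods avoided.

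So on CF, TF and AF no item needs reversal, and on the parent form only item 4 does. No printed form has an item 5 about receiving help.

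**Check against the stated range**

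Total = mean of six items coded 1–7; a reversed item is 8 − x.

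Participant forms:
- No reversal: all 1s give 1.0 and all 7s give 7.0. This reproduces the protocol's range.
- Items 4 and 5 reversed (SAP): all 1s give (4×1 + 2×7)/6 = 3.0; all 7s give (4×7 + 2×1)/6 = 5.0.

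Parent form, where raw item 4 is high when risk is low:
- Item 4 reversed: lowest risk 1.0, highest risk 7.0. This again reproduces the range.
- Items 4 and 5 reversed (SAP): lowest risk (5×1 + 7)/6 = 2.0; highest risk (5×7 + 1)/6 = 6.0.

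**Effect on a mean change, participant forms**

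Let the other four items change by d. The documents give no item-level data, so the movements of items 4 and 5 below are assumptions.

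| Items 4 and 5 | Correct change | Change under SAP rule | Share kept | True 1.0 shown as | True change needed to show 0.45 |
|---|---|---|---|---|---|
| Neither moves | 4d/6 | 4d/6 | 100% | 1.00 | 0.45 |
| Item 4 moves by d, item 5 fixed | 5d/6 | (4 − 1)d/6 = 3d/6 | 60% | 0.60 | 0.45/0.60 = 0.75 |
| Both move by d | 6d/6 | (4 − 2)d/6 = 2d/6 | 33% | 0.33 | 0.45 × 3 = 1.35 |
| Both move by −d/2 | (4 − 1)d/6 = 3d/6 | (4 + 1)d/6 = 5d/6 | 167% | 1.67 | 0.45 × 3/5 = 0.27 |

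If the only improvement is 1 point on each of items 4 and 5, the correct change is −2/6 = −0.33, but the SAP rule reports +0.33, a worsening.

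On the parent form only item 5 is wrong. All of the change is kept if item 5 does not move, and (5 − 1)/6 = 67% if all six items move equally in the risk direction.

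Little movement on item 5 is plausible, because participants "must be willing to continue avoiding exposure to peanuts and any other foods that they are allergic to throughout this study" (Protocol 5.1, criterion 8). The 33% row is therefore a lower-end illustration, not the expected effect.

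**The case against.** The best defence is that the sentence identifies its items by content, and that content matches only item 4 of the parent form. On this view it is a parent-form rule with a wrong item number, and the SAP's own statement that higher means more risk should stop anyone applying it to the other forms. That is probably how the sentence arose. It does not rescue the text: the sentence names no form, the FAIM measures the SAP lists by name are the participant forms, and even on the parent form reversing item 5 contradicts the protocol.

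A second objection is that items 5 and 6 carry no printed numeric codes, so the direction of item 5 rests on the order of the options together with the SAP's coding rule. That is correct. The inference is a natural one, but the codes exported from the handheld device are not in the documents and should be checked.

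A third is that the scenarios run from no effect through attenuation to inflation, so they fix no size. A shift in item 4 common to all arms, for example from the counselling every participant receives, would also largely cancel in a between-arm comparison. This stands. The same signs apply to between-arm differences in item change, so the distortion there depends on whether treatment itself moves items 4 and 5. The range failure (3.0 and 5.0 instead of 1 and 7) needs no such assumption.

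Finally, the reach is narrow. FAIM is an other secondary endpoint outside the testing strategy (Protocol 12.5.1), its p-values are unadjusted and for interpretation only (SAP 2.10.1.1), and FAIM-CF now concerns only 12-year-olds. All of that is true and limits how serious the error is.

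**Conclusion.** The concern holds. As written, the reversal rule is wrong on every printed FAIM form: two of six items are mis-signed on the child, teenager and adult forms, and one of six on the parent form. The participant total no longer spans 1 to 7 from best to worst status; uniform answers span only 3.0 to 5.0.

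The bias in the mean change cannot be fixed from the documents. Under the assumed scenarios, between 33% and 167% of the true change is reported, with no distortion if items 4 and 5 do not move. The conclusion assumes the sentence is applied literally and that item 5 is coded in the printed option order. Primary and key secondary endpoints, alpha control and power are untouched. It should be corrected because the FAIM results would otherwise be reported, and judged against 0.45 points, on a scale that contradicts its own definition.

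**What to change.** Replace the reversal sentence in SAP Section 2.10.1 with: *FAIM-CF, FAIM-TF and FAIM-AF: no item is reverse coded. FAIM in FAQLQ-PF Section D: item 4 only is reverse coded before the total score is calculated.*

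Then check the derivation code, and the device's export codes for item 5, against this rule. Re-derive FAIM totals only if any were already produced under the present sentence. The cost is one sentence and one programming check. No new data are needed, because the reversal (8 minus the item score) can be undone from the stored item responses.

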2.10.1.1 Patient-reported outcome analysis

All PRO scores will be summarized descriptively at Day 1, before and after the DBPCFC at Week 12 and Week 52 by treatment. Tabular summaries will present continuous PRO total and domain scores, plus change from baseline scores, as per Section 2.11.1. Summaries for change from baseline in FAQLQ and FAIM domain and total scores at Week 12 (before and after the DBPCFC) will also be provided by response status and treatment during DBPCFC at Week 12 (Responder/Non-responder at 600 mg of peanut protein). Change from baseline in SF-6Dv2 social function and mental health dimensions at Week 12 will be summarized by response status and treatment.

Change from baseline after Week 12 OFC Day 2 in FAQLQ and FAIM total scores will be analyzed using ANCOVA models with treatment group and region as fixed effects, and log-transformed total IgE at screening as well as respective PRO baseline value as covariates. Least Squares Mean differences, corresponding 95% CIs and p-values will be presented. All p-values presented from PRO inferential analyses are unadjusted and should be used to aid interpretation of the data only. Change from baseline before Week 12 OFC Day 1 in FAQLQ and FAIM total scores will be analyzed in a similar fashion.

All analyses will be performed on the FAS using observed data with no imputation of missing data.

2.11 Biomarkers

Peanut-specific IgE and IgG4 and SPT are analyzed as other secondary endpoints and described in [Section 2.6.2](#).

Additional details will be provided in a separate analysis plan targeting the analyses of biomarkers.

2.13 Interim analysis

There will be two analyses before the final database lock, in addition to the DMC analyses as described below.

Interim Analysis:

At the start of the study, recruitment will be restricted to 12-55 year old participants. When approximately 60 adolescent participants (defined as 12 -17 years of age) have completed all week 12 assessments, an interim analysis on [REDACTED] safety [REDACTED] data [REDACTED] will be performed (Section 2.9). Safety data (semi-blinded or unblinded) will only be generated for DMC review. [REDACTED]

Primary Analysis at Week 12:

The Primary Analysis will be performed once all participants have reached Week 12 in the study and completed its assessments or prematurely withdrawn from the study prior to Week 12. Formal testing of primary and key secondary endpoints will be performed according to testing strategy specified in Figure 2-1 with full alpha. Since the primary and key secondary objectives will be performed only for the Primary Analysis, adjustment to the overall type I error rate is not required. In addition, a Dose-Exposure-Response model to describe the responder rate and the factors impacting the response will be developed.

[figure not shown]
Table 2-2 provides the list of results that may be presented for the Primary Analysis at Week 12.

Table 2-2 Results presented at the Primary Analysis

Category	Analysis Description
OFC	Effect of 12 weeks of Ligelizumab: Analysis of the Proportion of Participants who Tolerated a Single Dose of ≥ 600 mg of Peanut Protein without Dose-Limiting Symptoms during DBPCFC at Week 12 using Logistic Regression Model (Full Analysis Set)
OFC	Effect of 12 weeks of Ligelizumab: Analysis of the Proportion of Participants who Tolerated a Single Dose of ≥ 1000 mg of Peanut Protein without Dose-Limiting Symptoms during DBPCFC at Week 12 using Logistic Regression Model (Full Analysis Set)
OFC	Effect of 12 weeks of Ligelizumab: Analysis of the Proportion of Participants who Tolerated a Single Dose of 3000 mg of Peanut Protein without Dose-Limiting Symptoms during DBPCFC at Week 12 using Logistic Regression Model (Full Analysis Set)
OFC	Effect of 4 weeks of Ligelizumab: Analysis of the Proportion of Participants who Tolerated a Single Dose of ≥ 1000 mg of Peanut Protein without Dose-Limiting Symptoms during DBPCFC at Week 12 (Full Analysis Set)
OFC	Summary of Proportion of Participants who Tolerated at Least the Single Dose of ≥ 600 mg Peanut Protein without Dose-Limiting Symptoms during DBPCFC at Week 12 (Full Analysis Set)
OFC	Proportion of Participants who Tolerated a Single Dose of ≥ 600 mg of Peanut Protein without Dose-Limiting Symptoms during DBPCFC at Week 12 by Timing of Study Termination Notice (Full Analysis Set)
OFC	Marginal Proportion of Participants who Tolerated a Single Dose of ≥ 600 mg of Peanut Protein without Dose-Limiting Symptoms during DBPCFC at Week 12 (Full Analysis Set)
OFC	Odds of Participants Developing Less Severe Level of Symptoms Evaluated by Maximum Severity of Symptoms at Any Challenge Dose of Peanut Protein up to and including 1000 mg during the DBPCFC Conducted at Week 12 (Full Analysis Set)

SPT	Summary of Skin Prick Test (undiluted peanut protein) and change from baseline by treatment group and across visits
SPT	Summary of Skin Prick Test (average dilutions peanut protein) and change from baseline by treatment group and across visits
PRO	FAQLQ-PF: Food Allergy Quality of Life Questionnaire – Parental Form (completed by parents of children aged 12)
PRO	FAQLQ-TF: Food Allergy Quality of Life Questionnaire – Teenager Form (completed by adolescents aged 13-17)
PRO	FAIM-TF: Food Allergy Independent Measure – Teenage Form (completed by adolescents aged 13-17))
PRO	FAQLQ-AF: Food Allergy Quality of Life Questionnaire – Adult Form (completed by adults aged 18-55)
PRO	FAIM-AF: Food Allergy Independent Measure – Adult Form (completed by adults aged 18-55)
Adverse Event	Number of adverse events due to Accidental Exposure (plus respective listing)
Event	Use of Epinephrine During and Outside of OFC
Safety	Overview of Treatment Emergent Adverse Events (Safety Set)
Safety	Exposure-adjusted TEAE tables for the entire population (Safety Set)
Listing	Deaths and SAEs by system organ class and preferred term (plus respective listing)
Safety	Treatment-emergent SAEs by primary system organ class
Safety	Treatment-emergent SAEs by preferred term (plus respective listing)
Safety	TEAEs by primary system organ class
Safety	TEAEs, by preferred term (plus respective listing)
Safety	TEAEs by preferred term and maximum severity
Safety	TEAEs leading to discontinuation by primary system organ class
Safety	TEAEs leading to discontinuation by preferred term (plus respective listing)
Safety	Treatment-emergent Adverse Events of Special Interest (AESI), by standardized MedDRA term (plus respective listing)
Safety	Number of AEs (n, %)
Safety	Newly occurring or worsening chemistry and hematology abnormalities (plus respective listing)
Safety	Newly occurring or worsening vital sign abnormalities (plus respective listing)
Safety	Adverse events for screen failures
Safety	Number of Subjects with Adjudicated Anaphylaxis Events (Safety Set) (plus respective listing)
Safety	Number of Subjects with Adjudicated CCV Events (Safety Set) (plus respective listing)
Safety	Number of Subjects with Adjudicated Neoplastic Events (Safety Set) (plus respective listing)
Safety	Number of AEs requiring Epinephrine treatment (n, %)
Disposition	Participant Disposition at Treatment Period (Randomized Set)
Set	Analysis Sets (Randomized Set)
Baseline	Subject Demographics (Randomized Set)
Baseline	Subject Baseline Characteristics (Randomized Set)

In addition, the following analyses will be presented.

DMC analyses:

The DMC will assess, at defined intervals, the progress of a clinical trial, safety data, and critical efficacy variables and recommend to the sponsor whether to continue, modify, or terminate a trial, as defined in the DMC charter. Analysis of selected efficacy variables will be provided only for the purpose of helping for safety evaluation. Such assessments do not inflate the Type I error for the primary efficacy hypothesis testing and thus no adjustment for multiplicity is required.

3 Sample size calculation

A total sample size of approximately 486 randomized participants is originally planned to achieve sufficient power for the primary and key secondary endpoints, and it provides adequate precision in estimating AE rates in this study. Due to the halt of recruitment, the sample size is now 211. This reduced sample size provides sufficient power for the primary endpoint.

Participants will receive one of three treatments (ligelizumab 240mg SCq4w, ligelizumab 120mg SCq4w, or placebo SCq4w) and will be randomized into five treatment arms with a ratio 2:2:2:2:1. At the start of the study, recruitment was restricted to participants 12-55 years old. Due to the recruitment halt, no other age groups were recruited.

